8.3.4 Digital Continuous and Triplicate 12-Lead ECG

Digital continuous ECG monitoring (e.g., Holter monitor) will be used at the time points specified in [Table 4](#) and [Table 7](#).

For all other time points where an ECG is required, computerized, good quality, 12-lead ECGs will be collected in triplicate and recorded. Recordings will be obtained in the supine position after the participant has rested comfortably for ≥ 5 minutes. If the initial reading is abnormal, the measurements will be repeated once to confirm the results.

The ECG tracing will be read locally. In the case of clinically significant findings, an ECG may be further reviewed by a board-certified cardiologist for a second opinion. Information should be recorded as to whether the ECG is normal or abnormal and, if deemed abnormal, what the abnormality is, and whether it is clinically significant or not clinically significant.

8.3.5 Clinical Laboratory Evaluations

Clinical laboratory safety testing, as detailed in [Section 10.2](#) will be collected at the time points described in the SoA. Safety laboratory assessments will be conducted by a certified laboratory. If the initial reading is abnormal, the measurements will be repeated once to confirm the results.

When applicable and feasible, blood sampling should follow evaluation of vital signs and ECGs to reduce any impact on these measurements.

8.3.6 Pregnancy Testing

For WOCBP, a serum pregnancy test will be done at Screening and at the final study visit or ET visit. Urine pregnancy tests will be done on Day -1 and at the visits noted in the SoA while on study. A positive urine pregnancy test will be confirmed, as soon as possible, with a serum pregnancy test. If a participant becomes pregnant while on study, refer to [Section 10.3.6](#) for instructions on how this should be reported.

8.4 Adverse Events

The definitions of AEs and SAEs and how they should be recorded, assessed, and reported can be found in [Section 10.3](#).

The Investigator and any qualified designees are responsible for detecting, documenting, and recording events that meet the definition of an AE or SAE, and remain responsible for following all ongoing AEs to the final study visit or ET visit, at a minimum, or until the Investigator and the Sponsor agree that further follow-up is not required. This includes events reported by the participant or, when appropriate, by a caregiver, surrogate, or the participant's legally authorized representative.

8.5 Pharmacokinetic Assessments

- Blood samples will be collected for measurement of plasma concentrations of WVE-006 and for potential analysis of metabolites as specified in the SoA ([Table 2](#) and [Table 6](#)). The actual date and time (24-hour clock time) of each sample will be recorded. Instructions for the collection and handling of biological samples will be provided by the Sponsor in a Laboratory Manual.
 - Plasma and urine samples for analysis of exposure to WVE-006 will be collected at the time points specified in [Table 2](#), [Table 3](#), and [Table 6](#). Samples will be collected at the following time points:
 - Period 1 Plasma PK: Samples will be collected predose within 30 min prior to dose, and postdose at 30 min (± 5 min), 1 hr (± 5 min), 2 hr (± 5 min), 4 hr (± 10 min), 6 hr (± 10 min), 8 hr (± 10 min), 12 hr (± 10 min), 24 hr (± 30 min), 36 hr (± 4 hr), and 48 hr (± 4 hr). A sample will be collected at each of the following visits: Days 8, 15, 22, 29, 36, 43, 50, 57, 64, 71, 78 (± 3 days), and Day 85 (± 5 days)/ET.
 - Period 1 Urine PK: Samples will be collected over 0-4 hr, 4-8 hr, 8-12 hr, 12-18 hr, 18-24 hr, 24-36 hr, and 36-48 hr.
 - Period 2 Plasma PK: Day 1 and Day 29 samples will be collected predose within 30 min prior to dose, and postdose at 30 min (± 5 min), 1 hr (± 5 min), 2 hr
-

(± 5 min), 4 hr (± 10 min), 6 hr (± 10 min), 8 hr (± 10 min), 12 hr (± 10 min), 24 hr (± 30 min), 36 hr (± 4 hr), and 48 hr (± 4 hr). A Day 15 predose sample will be collected at 30 min prior to dose. A sample will be collected at each of the following visits: Days 8, 21, 36, 43, 50, 57, 64, 71, 78, 85 (± 3 days) and Day 113 (± 5 days) / ET.

- Urine samples will be collected for measurement of concentration of WVE-006 and potential metabolites as specified in the SoA (Table 3). The following parameters will be estimated for the parent drug:
 - Ae: amount excreted in urine
 - Ae%: the percentage of the administered dose that is excreted in urine
 - Cum Ae%: cumulative Ae%
- The timing of sampling may be altered, and PK samples may be obtained at additional time points during the course of the study based on newly available data (e.g., to obtain data nearer the time of peak plasma concentration) to ensure appropriate monitoring of the PK profile.
- Blood samples will be used to evaluate the PK profile of WVE-006 assessed by the following PK parameters, if applicable:
 - AUC_{inf}: area under the curve from time 0 to infinity
 - AUC_{0-24h}: area under the curve from time 0 to 24 hours
 - AUC_{0-48h}: area under the curve from time 0 to 48 hours
 - AUC_{last}: area under the curve from time 0 to the last measurable concentration
 - AUC_{ext}: area under the curve extrapolated to infinity
 - AUC_{tau}: area under the curve over a dosing interval
 - C_{max}: maximum observed concentration
 - t_{max}: time to occurrence of C_{max}
 - t_{1/2}: terminal half-life
 - V_d: volume of distribution
 - CL: clearance
- Samples collected for analyses of WVE-006 plasma concentration may also be used to evaluate safety aspects arising during or after the study.
- PK information that would unblind the study will not be reported to investigative sites or blinded personnel until the study has been unblinded.

8.6 Pharmacodynamic Assessments

No PD assessments are included in this study.

8.7 Genetics

A blood sample for *SERPINA1* AAT genetic testing will be collected from all participants at Screening. Participants who do not wish to participate in the AAT genetic research will not be able to participate in the study.

Details on processes for collection, shipment, and destruction of these samples can be found in the Laboratory Manual.

8.8 Biomarkers

Biomarkers are not evaluated in this study.

8.9 Immunogenicity Assessments

Samples for antibodies to WVE-006 will be collected and may be analyzed in the future.

8.10 Health Economics

Health economics parameters are not evaluated in this study.

9 STATISTICAL CONSIDERATIONS

The final analyses will be conducted on data collected from participants after the study database is locked at the end of the study.

The statistical analysis plan will be created and finalized prior to the study database lock, and it will include more details of the planned statistical analysis for data that have been collected in this study. This section is a summary of the planned statistical analyses for the most important endpoints.

9.1 Sample Size Determination

The sample size for this Phase 1 study on HV was not calculated on the basis of statistical hypothesis testing. However, the number of participants (up to 40 in the SAD period and 8 in the multiple-dose period) is considered sufficient for this study to assess safety and tolerability for WVE-006 and to establish PK profile of WVE-006.

9.2 Analysis Populations

The following analysis sets will be defined for SAD and multiple-dose portions of the data analyses.

- Safety population will include randomized participants who have received at least 1 dose of study medication. The safety population will be the analysis set used for summaries of safety data collected in the respective period.
- PK population will consist of participants in the safety population with at least 1 post dose plasma concentration measurement.

9.3 Statistical Analyses

9.3.1 General Considerations

Data collected in the SAD and multiple-dose periods will be summarized and reported separately by dose groups (e.g., a given dose cohort will be a dose group). For the SAD period, data from participants who received placebo will be pooled across cohorts and summarized and presented as the “Placebo” dose group, which will be handled as one of the dose groups throughout this section.

Baseline for a SAD participant is defined as the last non-missing measurement collected prior to the administration of the single dose. Baseline for a multiple-dose participant is defined as the last non-missing measurement collected prior to the administration of study drug at Week 0 of multiple-dose period. Unless otherwise specified, the analyses described in the following sections apply to data collected in both SAD and multiple-dose periods.

Descriptive statistics (n, mean, standard deviation [SD], median, minimum and maximum values for continuous variables, and number and percentage of participants in each category for categorical variables) will be used for data summary by treatment group for each cohort.

9.3.2 *Disposition of Participants*

Screened participants are defined as any participant who signed the ICF, and the number of screened participants will be summarized by dose group.

Randomized participants consist of participants who signed the ICF and were subsequently randomly assigned. For each cohort, the number of randomized participants receiving placebo or WVE-006 will be tabulated.

The number and percentage of participants who discontinued from the study along with the reasons of discontinuation will be summarized by dose group for the safety population.

9.3.3 *Participants' Demographics and Baseline Characteristics*

Participants' demographics (age, gender, and race) and other baseline characteristics will be summarized by dose group for the safety population.

9.3.4 *Study Drug Exposure and Compliance*

The number of participants who received study drug will be summarized by dose group, and compliance (for Period 2) will also be summarized for the safety population.

9.3.5 *Analysis of Safety Data*

Safety analyses will be performed on the safety population.

9.3.5.1 *Adverse Events*

- An AE is any untoward medical occurrence in a clinical study participant, temporally associated with the use of study drug, whether or not considered related to the study drug.
- A treatment-emergent AE (TEAE) is defined as an AE not present before exposure to study treatment or any event already present that worsens in severity or frequency from the date of receiving first dose of study treatment to study completion or discontinuation.

General rules of analysis and reporting of AEs:

- AEs reported by Investigators will be coded to system organ class (SOC) and preferred term (PT) using the Medical Dictionary for Regulatory Activities (MedDRA).
 - For an event with multiple occurrences during the study, the event is only counted once in occurrence summary, the maximum severity is used when reporting the severity, the highest level of association will be used to characterize relatedness to study drug in reporting.
-

The number and percentage of participants who have at least a TEAE, a grade 3 or 4 TEAE, a study drug-related TEAE as judged by the Investigator will be summarized by dose group. In addition, the number and percentage of participants who have a TEAE that leads to study drug discontinuation or who died due to occurrence of a TEAE will also be summarized by dose group. The percentage for the aforementioned summaries will be calculated based on the number of participants in each dose group.

For each dose group, TEAEs will be presented by PT with the descending frequency of occurrence based on the pooled WVE-006 dose groups. In addition, TEAEs will also be summarized by SOC, PT, and the severity for each dose group.

The number and percentage of participants who had at least one SAE will be summarized by SOC and PT for each dose group. In addition, SAEs will be tabulated by dose group.

9.3.5.2 *Analysis of Clinical Laboratory Evaluations, Vital Signs, and ECG Parameters*

For laboratory parameters, change from baseline to maximum or minimum value during the study will be summarized by dose group for each parameter and reported by laboratory group, respectively. In addition, changes from baseline to each post-baseline visit will also be summarized by dose group.

Clinically significant changes will be summarized by dose group for vital signs.

A shift table presenting the shift from baseline to each post-baseline assessment in terms of Normal or Abnormal by dose group will be used to report ECG findings during the study.

9.3.6 *Pharmacokinetic Analysis*

PK data will be summarized descriptively and presented in both graphical and/or tabular formats.

PK parameters for WVE-006 and potential metabolites will be calculated using non-compartmental methods. PK parameters will be summarized for each WVE-006 dose group on the PK population using descriptive statistics: n, arithmetic mean, median, SD, minimum, maximum, and percent coefficient of variation (CV%); in addition, the geometric mean and geometric CV% will be reported for C_{max} and AUCs.

The PK parameters described in [Section 8.5](#) will be calculated for participants who receive at least one dose of WVE-006 during the study. Additional PK parameters may be evaluated if deemed necessary.

When appropriate, the correlation between QTcF and WVE-006 will be evaluated, and the results may be reported separately from the Clinical Study Report.

When appropriate, the identification and quantification of WVE-006 and its metabolites in urine will be performed and the results may be reported in a separate report.

9.3.7 *Interim Analyses*

No interim analyses are planned.

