	Pre-dose	Post dose												
	≤30 min prior to dose ^b	30 min (±5 min)	1 hr (±5 min)	2 hr (±5 min)	4 hr (±10 min)	6 hr (±10 min)	8 hr (±10 min)	12 hr (±10 min)	24 hr (±30 min)	36 hr (±4 hr)	48 hr (±4 hr)	(±3 days)	(±3 days)	(± 3 days)
Plasma PK ^a	X	X	X	X	X	X	X	X	X	X	X	X	X	Every week
CBC, CRP, fibrinogen, coagulation, albumin	X					X			X		X	X	X	Every week
Complement	X			X	X	X			X		X	X	X	Week 4 only
Cytokines ^c	X			X	X	X			X		X	X	X	Week 4 only

Abbreviations: CBC = complete blood count; CRP = C-reactive protein; PK = pharmacokinetic.

^a Sufficient plasma PK sample volume to cover both WVE-006 and potential metabolites. When applicable and feasible, PK blood sampling should follow evaluations of vital signs and ECGs to reduce any impact on these measurements.

^b Pre-dose laboratory results are NOT required prior to dosing.

^c Cytokine samples will be collected and may be analyzed for the following cytokines: IL-1β, IL-6, IL-10, IL-12/23 (P40), IFN-γ, TNF-α, MCP-1, and MIP-1β

Table 3 Urine PK Cumulative Collection Periods (Period 1)

Study Day/ Time Frame	Day 1					Day 2	Day 3
	0-4 hr	4-8 hr	8-12 hr	12-18 hr	18-24 hr	24-36 hr	36-48 hr
Urine PK ^a	X	X	X	X	X	X	X

Abbreviation: PK = pharmacokinetic.

^a Urine for PK assessments will be collected continuously through 48 hours per the stated time periods. For each of these time periods, total volume will be captured in the electronic case report form (eCRF).

Table 4 Triplicate ECG Assessment Time Points (Period 1)

Study Day/ Specific Time	Day 1											Day 2	Day 3
	Pre-dose			Post dose									
	-45 min ±5 min	-30 min ±5 min	-15 min ±5 min	30 min ±5 min	1 hr ±5 min	2 hr ±5 min	4hr ±10 min	6hr ±10 min	8hr ±10 min	12hr ±10 min	24hr ±30 min	48hr ±4 hr	
ECG ^a	X	X	X	X	X	X	X	X	X	X	X	X	X

Abbreviations: ECG = electrocardiogram

^a Digital ECG monitoring for at least 48 hours from Day -1 through Day 2. Additional triplicate ECG measurements at the time points listed here.**Table 5 Overall Schedule of Assessments (Period 2)**

	Screening Period ^a	Treatment Period								Follow-up Visit				ET
Visit	1	2				4	6			3, 5, 7, 8, 9, 11, 12, 13, 14, 15, 16	10	14	15	
Study Week	Week -4 to Week 0	Week 0 CRU Stay				Week 2	Week 4 CRU Stay			Week 1,3, 5, 6, 7, 9, 10, 11	Week 8	Week 12	Week 16	

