Cytokines ^c	X			X	X	X			X Day 2 only		X Day 3 only	Weeks 1, 5, 6, and 8 only

Abbreviations: CBC = complete blood count; CRP = C-reactive protein; PK = pharmacokinetic.

^a Sufficient plasma PK sample to cover both WVE-006 and potential metabolites. When applicable and feasible, PK blood sampling should follow evaluations of vital

signs and ECGs to reduce any impact on these measurements.

^b Pre-dose laboratory results are NOT required prior to dosing

^c Cytokines samples will be collected and analyzed for: IL-1 β , IL-6, IL-10, IL-12/23 (P40), IFN- γ , TNF- α , MCP-1, and MIP-1 β

Table 7 Triplicate ECG Assessment Time Points (Period 2)

Study Day/ Specific Time	Day 1			Days 1 and 29							Days 2 and 30	Day 3
	Pre-first dose			Post first and last doses								
	-45 min ±5 min	-30 min ±5 min	-15 min ±5 min	30 min ±5 min	1 hr ±5 min	2 hr ±5 min	4hr ±10 min	6hr ±10 min	8hr ±10 min	12hr ±10 min	24hr ±30 min	48hr ±4 hr
ECG ^a	X	X	X	X	X	X	X	X	X	X	X	X

Abbreviations: ECG = electrocardiogram

^a Digital ECG monitoring for at least 48 hours from Day -1 through Day 2 and at least 24 hours through first day of last dose (Day 29). Additional triplicate ECG measurements at the time points listed here.

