3 OBJECTIVES, ENDPOINTS, AND ESTIMANDS

Table 8 Study Objectives and Endpoints for WVE-006-001

Primary Objective:	Primary Endpoint:

 To evaluate the safety and tolerability of WVE-006 	
 Incidence of treatment emergent adverse events (TEAEs), related TEAE, severe TEAE, serious TEAE Changes in safety assessment parameters (i.e., physical exam, vital signs, clinical laboratory results, ECGs (including any changes to QTcF)) Tolerability based on incidence of discontinuation due to TEAEs
Secondary Objective:	Secondary Endpoints:

 To evaluate the PK of WVE-006 after a single dose in healthy participants To evaluate the PK of WVE-006 after multiple doses in healthy participants 	
 PK parameters of WVE-006 in plasma, including AUC_{inf}, AUC_{0-24h}, AUC_{0-48h}, AUC_{last}, C_{max}, t_{max} PK parameters of WVE-006 in plasma following the first and last doses, including AUC_{tau}, AUC_{0-24h}, AUC_{0-48h}, AUC_{last}, C_{max}, t_{max}
Exploratory Objectives:	Exploratory Endpoints:

 To evaluate urine excretion of WVE-006 	
 Ae, Ae%, and cumulative Ae% (cum Ae%) for parent drug, as well as potential metabolites in urine

Abbreviations: Ae=amount excreted; AUC=area under the curve; C=concentration; ECG=electrocardiogram; PK=pharmacokinetic; t=time; TEAE=treatment-emergent adverse event

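### The default last-value baseline leaves two of the three scheduled pre-dose triplicate ECG sets unused, which generally makes QTcF changes noisier than the collected data allow

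*Combined protocol and SAP*

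**What the plan says.** **Baseline.** Section 9.3.1 sets one rule for each period, covering all variables. Period 1: "Baseline for a SAD participant is defined as the last non-missing measurement collected prior to the administration of the single dose". Period 2: "Baseline for a multiple-dose participant is defined as the last non-missing measurement collected prior to the administration of study drug at Week 0". Neither Section 8.3.4 nor Sections 9.3.1 to 9.3.6 states a separate ECG baseline, or says how replicates or pre-dose sets are combined.

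**Schedule.** Table 4 (Period 1) and Table 7 (Period 2, first dose) list three pre-dose triplicate times: -45, -30 and -15 minutes.

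**Use.** The ECG item of the primary endpoint in Section 3 (Table 8) reads "ECGs (including any changes to QTcF", with the bracket closing there. Section 9.3.5.2 specifies one ECG analysis, a Normal/Abnormal shift table. Section 9.3.6 adds an evaluation of QTcF against WVE-006, when appropriate and possibly reported separately. Sections 4.1 and 4.3 allow an optional Cohort 6 for concentration-QTc.

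**Recording method.** Section 8.3.4 states: "Digital continuous ECG monitoring (e.g., Holter monitor) will be used at the time points specified in" Tables 4 and 7. For all other times it says "computerized, good quality, 12-lead ECGs will be collected in triplicate and recorded". The footnotes to Tables 4 and 7 describe continuous monitoring and then "Additional triplicate ECG measurements at the time points listed here". Footnote j of Table 1 and footnote k of Table 5 agree with those footnotes.

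**The concern.** The schedule pays for three pre-dose triplicate sets, but the only baseline rule stated uses the last of them. Error in a baseline is carried into each change score computed from it. With up to 6 active participants per cohort, avoidable noise in QTcF changes is unwelcome, both in descriptive summaries and in a concentration-QTc evaluation. A baseline that is not fixed before the data are seen also leaves a choice among several candidates.

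The recording-method text adds a smaller problem. It is unclear whether QTcF at the table times comes from the continuous recording or from the triplicate 12-lead tracings, and so whether visits outside those tables are compared with a baseline from the same method.

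**Working it through.** The plan gives no SD, correlation, alpha or power for QTcF, so there is no figure to reproduce. The calculation compares two baselines.

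**Inputs**
- From the documents: three pre-dose triplicate sets (Tables 4 and 7); last-value rule (Section 9.3.1); up to 6 active participants per cohort (Section 4.1.2).
- Assumed: *s*, the within-participant SD of one triplicate mean, and *r*, the correlation between the deviations of the pre-dose sets.

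**Step 1. Post-dose deviation independent of the pre-dose ones**
- Last set as baseline: Var(change) = s² + s² = 2s², SD = 1.414s.
- Mean of three sets: Var(change) = s²[1 + (1 + 2r)/3].

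| r | Variance, mean of three | SD | Reduction in SD from 1.414s |
|---|---|---|---|
| 0 | 1.333s² | 1.155s | 18.4% |
| 0.25 | 1.500s² | 1.225s | 13.4% |
| 0.5 | 1.667s² | 1.291s | 8.7% |
| 0.75 | 1.833s² | 1.354s | 4.3% |
| 0.9 | 1.933s² | 1.390s | 1.7% |

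The best case, r = 0, in milliseconds for assumed s = 5, 8 and 10 ms:
- SD of a change: 7.1 to 5.8, 11.3 to 9.2, and 14.1 to 11.5.
- Standard error of a cohort mean with n = 6: 2.9 to 2.4, 4.6 to 3.8, and 5.8 to 4.7.

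**Step 2. Serial correlation that extends to the post-dose reading**

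Let two sets *t* minutes apart have correlation c(t) = (1 - g)ρ^(t/15), where ρ is the correlation per 15 minutes and g is the share of independent noise. For a reading at 30 minutes, in units of s²:
- Last set: 2[1 - c(45)].
- Mean of three: 1 + [3 + 4c(15) + 2c(30)]/9 - (2/3)[c(45) + c(60) + c(75)].

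With ρ = 0.9 and g = 0:
- Last set: 2(1 - 0.729) = 0.542.
- Mean of three: 1 + 0.913 - 1.317 = 0.596.
- SD ratio: √(0.596/0.542) = 1.049, so averaging raises the SD by 4.9%.

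With ρ = 0.9 and g = 0.25:
- Last set: 0.907. Mean of three: 0.781.
- SD ratio: 0.928, so averaging lowers the SD by 7.2%.

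Over ρ = 0.5, 0.8, 0.9 and 0.95 and post-dose times from 30 minutes to 24 hours:
- g = 0.25 or 0.5: averaging lowered the SD at every time tested, by about 5% to 15%.
- g = 0 and ρ = 0.5: averaging lowered the SD by 8.5% to 10.2%.
- g = 0 and ρ = 0.8 to 0.95: the change was +1.1% to +6.9% at 30 minutes and -1.7% to +3.5% at 1 hour. At 24 hours it was a reduction of 1.1% to 4.3%.

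**Step 3. Recording method**

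Tables 4 and 7 contain both the pre-dose times and the early post-dose times. Whichever reading of Section 8.3.4 is taken, these come from the same method as each other. A mismatch can arise mainly outside those tables: Day 85 in Table 1, and Days 57, 85 and 113 in Table 5. It can also arise at 48 hours on Day 3, which both tables list although their footnotes describe monitoring from Day -1 through Day 2.

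**The case against.** **The ECG analysis named is categorical.** Section 9.3.5.2 specifies a Normal/Abnormal shift table, and it describes changes from baseline for laboratory parameters only. This stands: the variance arithmetic does not apply to a shift table, which is touched only through its baseline category. But the endpoint is worded as changes to QTcF, Section 9.3.1 promises descriptive statistics for continuous variables, and Section 9.3.6 foresees a QTcF evaluation. The missing numeric QTcF summary is itself a gap.

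**Section 9 is a summary, with detail left to a SAP finalized before database lock.** Also true, and the rule is general rather than a deliberate ECG decision. The baseline for the concentration-QTc evaluation is unstated rather than fixed at the last set. Even so, the protocol already states a rule, and that rule governs ECG until something replaces it.

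**Stronger readings that the documents do not support**
- *Every QTcF change becomes noisier.* Step 2 shows that this is not guaranteed.
- *Averaging is worth 50% more participants.* That is 2/(4/3) = 1.5 and needs r = 0. The figure is 20% at r = 0.5 (2/1.667) and about 3.4% at r = 0.9 (2/1.933). It also treats all variation in change as reading error. If true changes vary between participants with variance s², it falls to 29% even at r = 0 (3/2.333).
- *Baseline is one tracing, so averaging halves the variance.* The tables are titled as triplicate time points, so the triplicate is the natural unit. That comparison also averages the post-dose triplicate but not the baseline one, an asymmetry that the text does not contain.
- *Pre-dose and early post-dose QTcF come from different recorders.* Step 3 shows that both sit in the same tables.

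**Conclusion.** The point holds. As written, the plan leaves the -45 and -30 minute sets out of the ECG baseline in both periods, although using them costs nothing.

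The size is uncertain. The reduction in the SD of a QTcF change runs from about 18% (uncorrelated sets) through 9% (r = 0.5) to 2% (r = 0.9), assuming post-dose deviations independent of pre-dose ones. The gain can vanish or reverse at the earliest post-dose times if serial correlation is strong and there is no independent noise. Confidence is high that the rule is missing and moderate about how much averaging gains. The sample size does not rest on hypothesis testing (Section 9.1), so no power figure changes.

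The recording-method wording is a separate, smaller inconsistency. It matters mainly for visits outside Tables 4 and 7.

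**What to change.** 1. In Section 9.3.1 or the SAP, for both periods: define the baseline for ECG parameters as the mean of the three triplicate means at -45, -30 and -15 minutes before the first dose, and use the triplicate mean at each post-dose time.
2. Apply the same baseline to the concentration-QTc evaluation in Section 9.3.6.
3. Add to Section 9.3.5.2 a numeric summary of QTcF change from baseline by dose group and time, and say which pre-dose reading sets the baseline category of the shift table.
4. Reconcile Section 8.3.4 with the footnotes of Tables 1, 4, 5 and 7, so that the baseline and the later visits outside Tables 4 and 7 (for example Day 85 and Day 113) take QTcF from the same recording method.

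The cost is a few sentences and one additional table, with no new data or visits. The wording should be settled before the data are seen.
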